patient partners) to score the answers from 1-5 based on accuracy, safety and a metric known as the global quality score. The validity and reliability of these metrics were established during several rounds of testing with the raters in addition to literature evidence. The LLM chatbot is not a learning model and will only utilize existing resources gathered for the KiT study. Although, since LLMs are stochastic in nature – i.e., may generate different answers to the same question at different times – we will ask each question 3 times. In addition, we want to test the use of LLMs as evaluators of the quality of answers. In order to do this, we will ask an LLM evaluator to also grade the answer to questions based on the aforementioned criteria, and compare this rating to the human raters. If successful, we plan to have the LLM evaluator continuously assess the questions asked by participants for any sensitive information (e.g., pertaining to suicidal ideation) and the quality of answers given, and flag any potentially harmful case for human review during the study.

It should also be noted we have previously assessed a prototype version of the KiT LLM and an LLM Evaluator (using GPT-4 accessed through UHN's Microsoft Azure subscription) on a set of synthetic questions, with promising results. We are in the process of improving these applications based on feedback from this initial assessment. Examples of these updates include stronger language on recommending visits to the emergency department in certain cases and explicit instructions to consider suicidal ideation when flagging potentially sensitive questions. We plan to test updated versions of the KiT and Evaluator LLMs with the questions already asked by participants during the study.

The English safety testing has been completed and the results are below. Once this amendment is approved them the LLM chatbot will be incorporated in Ontario sites.

English safety testing conclusions (please see accompanying PowerPoint presentation in CTO application)

Common questions to all raters (39 participant questions +12 synthetic questions)

- When considering the full set of questions (39 participant, 12 synthetic), the KiT LLM seems to perform well, with high scores in most metrics, particularly Safety.
- Overall the LLM Evaluator seems to act as, or more, conservative than most human raters (the exception being Patient Partner 2, which was slightly more conservative in general).

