 - o There is some subjectivity in how clinicians and patient partners perceive the quality of the KiT LLM answers. For example, while PP2 indicated (few) major safety concerns, PP1 did not indicate any safety concerns. No major safety concerns were also indicated by clinicians.
- GQS metric, which is largely a measure of practicality, was scored lower by human raters (although still with high scores. This is not a major concern to us, as Accuracy and specially Safety scores were high, ***indicating the answers are factual and, most importantly, do not do major harm to participants.***

Participant questions – subset of common questions (39 participant questions)

- When only looking at the common subset of participant questions, KiT LLM still maintains scores in the high-end for all metrics.
- Human raters seem to be more conservative than the LLM Evaluator for most metrics, but not by much.
 - o As before, there is some variability between raters. For example, the LLM Evaluator tends to be more conservative than PP1 for all metrics, and slightly less for PP2. Overall scores for all metrics are still high.
- In particular, the LLM Evaluator seems well calibrated for the Safety metric, being as conservative as the human raters in most cases.

- In general, metric scores show promising results by the human raters – again, in particular with the Safety metric.

Participant questions - all questions, inclusion unique ones per rater (45 questions)

- When considering the entire set of participant questions (including unique questions asked to each rater), the conclusions are similar to when considering the common set of participant questions – which is expected, since the common set is a subset of the questions asked in these analyses.

In general, the human raters are slightly more conservative than the LLM Evaluator, but not by much. The LLM Evaluator seems to be well-calibrated for the Safety metric in particular, being close to the human raters in the scoring.

LLM Evaluator (using GPT-4 accessed through UHN's Microsoft Azure subscription)

- Shows to be well-calibrated to flag answers to humans, especially pertaining to Safety.
- Participant answers, will be flagged if they score an Accuracy/GQS score ≥ 3 , and with a Safety score ≥ 2 (any minor or major concerns).

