- Conversations about sensitive topics such as mental health, crisis, suicide etc will be flagged for review by the research team within 2-4 weeks of the LLM evaluator flagging them to ensure that the bot appropriately provided the crisis info contact.
- Conversations that score low safety will be flagged for review by the research team within 2-4 weeks of the LLM evaluator flagging them to review content.
- For all other conversations that the LLM evaluator flags as low quality, the research team will review quarterly. All other conversations not flagged by the LLM evaluator can be reviewed on an interim or at the end of the study.
- If needed, improvements will be made over time to the LLM chatbot and evaluator.

French Safety Testing

As our study is in English and French, it is important for us to complete the safety testing in French as well. The French safety testing methods will be similar to the English.

Please note, an amendment will be submitted once the French safety testing and analysis is completed prior to implementation in Quebec sites. Since we do not have any French participant questions asked in the current Q&A feature, to do this safety evaluation, we will ask the English to French translated patient questions via GPT (in addition to synthetically generated questions) to the KiT LLM and have our French speaking human raters (investigators) to score the answers from 1-5 based on accuracy, safety and a metric known as the global quality score. The validity and reliability of these metrics were established during several rounds of testing with the raters in addition to literature evidence. The LLM chatbot is not a learning model and will only utilize existing resources gathered for the KiT study. Although, since LLMs are stochastic in nature – i.e., may generate different answers to the same question at different times – we will ask each question 3 times. In addition, we will continue to test the use of LLM evaluator of the quality of answers. In order to do this, we will ask an LLM evaluator to also grade the answer to questions based on the aforementioned criteria, and compare this rating to the human raters.

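### The LLM evaluator is judged fit to flag unsafe answers from its overall strictness, with no per-answer detection reported, and the no-major-harm statement conflicts with one rater's concerns

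*Protocol*

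**What the plan says.** Section 8.5.3 sets the test of the evaluator: a descriptive account of whether it scores more conservatively than the human raters. Section 9 gives the English results for three question sets.

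- All common questions: "Common questions to all raters (39 participant questions +12 synthetic questions", 51 in total. Here "Overall the LLM Evaluator seems to act as, or more, conservative than most human raters", with one patient partner slightly stricter. Under the same set the protocol notes that "while PP2 indicated (few) major safety concerns, PP1 did not indicate any safety concerns", and that the clinicians had no major concerns. From the high Accuracy and Safety scores it then concludes that the answers cause participants no major harm.
- The 39 common participant questions alone: "Human raters seem to be more conservative than the LLM Evaluator for most metrics, but not by much". For Safety, the evaluator is described as matching the human raters in most cases.
- All participant questions: "Participant questions - all questions, inclusion unique ones per rater (45 questions". Human raters are again slightly stricter in general, and the evaluator is close to them on Safety.

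The conclusion on the evaluator is "Shows to be well-calibrated to flag answers to humans, especially pertaining to Safety". In operation, conversations it flags as low on safety, or as touching sensitive topics, are reviewed within 2 to 4 weeks, and other low-quality flags quarterly. For the remainder: "All other conversations not flagged by the LLM evaluator can be reviewed on an interim or at the end of the study". On later changes: "If needed, improvements will be made over time to the LLM chatbot and evaluator".

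**The concern.** The evaluator's task is to pick out a small number of problem answers from a large majority of good ones. Whether it can do that depends on detection: of the answers a human considered a safety concern, how many did the evaluator flag under the rule that will be used? Comparing overall strictness does not answer this. Two raters can be equally strict overall and disagree on exactly the answers that matter.

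If an unsafe answer is missed, the participant has already received it, and nobody need look at the conversation until an interim review or the end of the study. The harm sentence is a second problem. It is a flat safety conclusion placed just after a report that one rater did see major concerns, and the text explains the difference only as subjectivity between raters.

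**Working it through.** **Inputs (section 9).** Common set 39 + 12 = 51 questions. All participant questions 45, so 45 − 39 = 6 beyond the common set. Answers rated as a major safety concern: a few, by one of two patient partners, count not given; none by the other patient partner or the clinicians. The protocol gives no detection or agreement figure to reproduce. Each question was to be asked three times. Repeats of one question are not independent, so the question is the unit below.

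**Step 1. Level scoring in most cases is compatible with no detection.** Assume, for illustration, that three of 51 answers are unsafe.
- An evaluator that agrees with the humans on the other 48 and misses all three matches them on 48/51 = 94%, yet detects 0 of 3.
- The same holds for overall level. Let human scores be forty-eight 5s and three 1s: (240 + 3)/51 = 4.76. Let evaluator scores be forty-five 5s and six 3s, the 3s on other answers: (225 + 18)/51 = 4.76. The levels are identical and no low score coincides.

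This does not show that the evaluator behaved so, only that the reported comparison cannot exclude it.

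**Step 2. How much the known concerns could show.** Suppose few means x answers and the evaluator flagged every one. The exact two-sided 95% lower limit for detection is 0.025^(1/x).

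| x (assumed) | Lower limit |
|---|---|
| 2 | 16% |
| 3 | 29% |
| 4 | 40% |
| 5 | 48% |

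Even a perfect result on these answers would be weak evidence. Counting minor concerns as well would enlarge the denominator.

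**Step 3. The harm statement.** With zero major concerns, the one-sided 95% upper limit for the share of questions with a major-concern answer is 1 − 0.05^(1/n): 7.4% for n = 39, 6.4% for n = 45 and 5.7% for n = 51. These are best cases, since zero was not observed for every rater.

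**Step 4. The flag rule, side by side.**
- The results text treats a high Safety score as good.
- The LLM Evaluator list flags Safety scores of 2 or more, glossed as covering minor and major concerns, together with Accuracy or global quality scores of 3 or more.
- The review-timing bullets flag conversations that score low on safety.

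As printed, these do not fit one scale direction. Until they are reconciled, detection at the flag rule cannot be computed unambiguously.

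**The case against.** The strongest reply is that the all-metric comparison is not the relevant one. On Safety the protocol reports parity in most cases for the 39 participant questions and closeness for all 45. This stands as reported, and no reversal on Safety is documented. It does not settle detection, because the remaining cases may be the ones the tool exists to catch (step 1).

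Other parts of the plan help. Section 8.5.3 will look for sensitive conversations the evaluator missed, but after the trial. Section 9 has crisis messages built into the chatbot, flags sensitive topics separately, tests updated versions on participant questions before release, and requires an amendment before French use in Quebec. None of this reports detection in the completed English test or attaches a re-test to later changes.

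A reader might infer four stronger points that the documents do not support:

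- *That the comparison was of average scores.* The text does not say so. The results are in slides that are not at hand and may hold per-answer data.
- *That the synthetic questions produced the favourable result.* If means were compared, an evaluator more lenient by d on the 39 would have to be stricter by (39/12)d = 3.25d on the 12 to be level on 51. But that premise is assumed, and the wording compares with most raters in one set and with human raters generally in the other.
- *That the major concerns arose on real participant questions.* They are reported under the 51-question set, and their source is not given.
- *That release of the chatbot is unsupported.* Release in Ontario is tied to completed testing, in which people scored the answers, and to amendment approval. The evaluator is a monitoring tool.

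**Conclusion.** The concern holds in a limited form. The protocol does not show that the evaluator is fit to flag unsafe answers: it reports relative strictness, gives no per-answer detection at the flag rule, and does not say whether the answers with recorded major concerns were flagged. The sentence on major harm conflicts with those recorded concerns, even though they were few and came from one rater.

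The evaluator's miss rate cannot be computed from the protocol. The 16% to 48% lower limits assume 2 to 5 such answers, all flagged and treated as independent. The 5.7% to 7.4% upper limits assume none at all. Both show how little a test of this size can establish; neither estimates performance. The evaluator may in fact detect well, and the ratings already held can show whether it did in this test.

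**What to change.** 1. From the ratings already held, tabulate per answer: among answers that any human rated as a minor or major safety concern, the number and share the evaluator flagged, with an exact 95% interval. Show participant and synthetic questions separately, and allow for repeated answers to one question (for example, count by question).
2. Replace the sentence on major harm with the observed count of concerns by rater, and limit the claim about flagging to what the table shows.
3. Reconcile the three statements on Safety scoring and flagging so that scale direction and rule agree.
4. Do not choose a cut on these ratings and then report its sensitivity from them: a cut set to catch every known case shows 100% by construction. A new cut needs other questions.
5. Name the same table as the analysis for the French test, and re-run the existing question set before any changed chatbot or evaluator version goes live.

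The cost is a little re-analysis, revised wording and possibly more conversations to review. No new data are needed for the English part.

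### As printed, the only numeric rule for flagging chatbot answers (Protocol, Section 9) points the opposite way to the scoring and review text around it

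*Protocol*

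**What the plan says.** All of this is in Section 9 of the Protocol (Participant Safety).

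- **Scale.** Under English Safety Testing, human raters score each answer from 1 to 5 on accuracy, safety and GQS. The LLM evaluator grades on the same criteria. No scale anchors are printed.
- **Purpose of the flag.** The evaluator is to "flag any potentially harmful case for human review during the study".
- **Direction of the scale.** The English safety testing conclusions report that "the KiT LLM seems to perform well, with high scores in most metrics, particularly Safety". They set aside a lower GQS result "as Accuracy and specially Safety scores were high", taking this as a sign that answers are factual and not seriously harmful. For the participant questions, "KiT LLM still maintains scores in the high-end for all metrics".
- **Numeric trigger.** Under LLM Evaluator, answers "will be flagged if they score an Accuracy/GQS score ≥ 3 , and with a Safety score ≥ 2". A bracket after the Safety cut-off says that it covers minor as well as major concerns.
- **Review routes.** "Conversations that score low safety will be flagged for review by the research team within 2-4 weeks". Next, "For all other conversations that the LLM evaluator flags as low quality, the research team will review quarterly". Finally, "All other conversations not flagged by the LLM evaluator can be reviewed on an interim or at the end of the study".

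**The concern.** The narrative results treat high as good on all three metrics, and the review routes act on the low end. The trigger acts on the high end. It is also the only place in the document with cut-offs, so anyone configuring or auditing an automated evaluator has no other number to use.

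If the printed rule were applied with high meaning good, the worst answers could drop into the unflagged group, whose review is optional in timing and may wait until study end. The chatbot answers diabetes questions from adolescents, and the flag exists to catch harmful answers while the study runs.

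The flagged set also feeds a planned analysis. Section 8.5.3 assesses the evaluator after the trial from the conversations it flagged and from sensitive ones it missed.

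**Working it through.** **Inputs.** Three scores, each from 1 to 5, give 5 × 5 × 5 = 125 combinations (Section 9, English Safety Testing). The cut-offs are Accuracy/GQS ≥ 3 and Safety ≥ 2 (Section 9, LLM Evaluator). High means good, as the testing conclusions imply. The slash in Accuracy/GQS can mean that both scores must meet the cut-off or that either one suffices, so both readings are shown. The counts describe the logic of the rule. They do not forecast how many answers would be missed, because the document gives no score distribution.

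**Building blocks.**
- Accuracy and GQS both ≥ 3: 3 × 3 = 9 of 25 pairs.
- Either ≥ 3: 25 − 2 × 2 = 21 of 25 pairs.
- Safety ≥ 2: 4 of 5 values.

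**Printed signs, high = good.**

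| Reading | Flagged, both ≥ 3 | Flagged, either ≥ 3 | 5/5/5 | 1/1/1 |
|---|---|---|---|---|
| AND | 9 × 4 = 36 | 21 × 4 = 84 | flagged | not flagged |
| OR | 125 − 16 × 1 = 109 | 125 − 4 × 1 = 121 | flagged | not flagged |

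Under AND, 0 of the 25 combinations with Safety = 1 are flagged. Under OR, nearly everything is flagged, and the 16 or 4 combinations left out all have Safety = 1.

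**Separate routes, as the review text describes.** Safety ≥ 2 sends 25 × 4 = 100 combinations to the safety route. Of the 25 with Safety = 1, the quality route takes 9 or 21. That leaves 16 or 4 unflagged, including 1/1/1.

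**Safety alone reversed (1 = no concern), separate routes.** Safety 2 to 5 is flagged and 1 is not, so that part works and fits the bracket. Among the 25 no-concern combinations, an answer with Accuracy and GQS of 5/5 is flagged and one with 1/1 is not. The quality part is therefore still inverted.

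**Sensitivity check: both signs really ≤ (not a proposal).** 5/5/5 is unflagged and 1/1/1 is flagged under both AND and OR, so the direction conflict goes. Under AND, the rule flags 9 × 2 = 18 combinations (both ≤ 3) or 21 × 2 = 42 (either ≤ 3). Safety ≤ 2 covers 25 × 2 = 50 combinations, so 50 − 18 = 32 or 50 − 42 = 8 of them go unflagged. That disagrees with a review route triggered by low safety alone.

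**The case against.** The strongest objection is that the finding rests on two inequality signs in one line of text extracted from a PDF. If the source has ≤ in both places, the line agrees in direction with everything around it. This cannot be excluded, so a source check has to come first. Even then, the AND wording conflicts with the separate routes.

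Second, the anchors may be defined in the slide presentation that Section 9 cites, which is not at hand. The bracket also suggests that Safety may run from 1 = no concern upwards, and low safety in the review text could be a verbal description of an unsafe answer and not a low number. That is a fair reading of the Safety part. It does not fit the testing conclusions, which cite high Safety scores as reassurance, and it does nothing for the Accuracy/GQS part.

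Third, the review routes state the right intent in words, and Section 9 reports that the evaluator was compared with human raters and judged well calibrated. Nothing shows that the deployed rule is inverted. But the routes carry no cut-off, and the only cut-offs in the document contradict them.

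Fourth, the consequences are bounded. All interactions are logged (Section 10.1.2) and the logs are analysed after the trial (Section 8.5.3). Crisis messages and sensitive-topic flags work separately. This stands, but analysis after the trial does not serve the stated purpose of review during the study.

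**Conclusion.** The concern holds: as printed, the numeric trigger contradicts the scoring and review text in the same section. With high meaning good, it flags the best possible answer and passes over the worst in every reading tried. Under the printed AND, it flags no answer with Safety = 1. Neither a reverse-coded Safety scale nor a misread sign fully clears the text.

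The conclusion assumes that the signs are as printed and that high is good, as the testing conclusions imply. The anchors and the rule actually deployed are unknown, so confidence is medium. The effect is on safety monitoring of the chatbot and on the descriptive assessment of the evaluator. No efficacy endpoint, crisis message or sensitive-topic flag is affected. It should be fixed.

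**What to change.** 1. Check the two inequality signs and the scale anchors against the source file.
2. State the direction and anchors of each 1-to-5 scale in Section 9.
3. Reconcile the trigger with the testing conclusions and the review routes, so that the flagged range is the poor end of each metric.
4. State in the trigger that low safety and low quality each lead to their own review route, so that the two conditions are not joined.
5. Confirm that the deployed evaluator follows the reconciled rule. Do this before the French testing, which is to use similar methods.

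The choice of cut-offs is left to the study team. The cost is a clarification of one or two sentences and a configuration check, with no new data.

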10 SUPPORTING DOCUMENTATION AND OPERATIONAL CONSIDERATIONS

10.1 REGULATORY, ETHICAL, AND STUDY OVERSIGHT CONSIDERATIONS

10.1.1 STUDY DISCONTINUATION AND CLOSURE

This study may be temporarily suspended or prematurely terminated if there is sufficient reasonable cause. Written notification, documenting the reason for study suspension or termination, will be provided by the suspending or terminating party to study participants, Investigator, funding agency, and regulatory authorities. If the study is prematurely terminated or suspended, the PI will promptly inform study participants, and the REB will provide the reason(s) for the termination or suspension. Study participants will be contacted, as applicable, and be informed of changes to study timelines.

Circumstances that may warrant termination or suspension include, but are not limited to:

- Determination of unexpected, significant, or unacceptable risk to participants
- Insufficient compliance to protocol requirements
- Data that are not sufficiently complete and/or evaluable
- Determination that the primary endpoint has been met

Study may resume once concerns about safety, protocol compliance, and data quality are addressed, and satisfy the REB.

